Summary Table of Periodontal Examination (BOP, GI, Tooth mobility and PCR)

	
15.3.7.7 Listing for Tooth Mobility - As Exposed Set -
 
15.3.7.8 Listing for Periodontal Treatment/Maintenance - As Exposed Set -
 
15.1.7.10 Scatter Plot of Gingival Index vs Visit by Product Use Categories - As Exposed Set -
 
15.1.7.11 Scatter Plot of Gingival Index vs Visit by Initial Full-Mouth Pocket Depth (mm) - As Exposed Set -
 
15.1.7.12 Scatter Plot of Tooth Mobility vs Visit by Product Use Categories - As Exposed Set -
 
15.1.7.13 Scatter Plot of Tooth Mobility vs Visit by Initial Full-Mouth Pocket Depth (mm) - As Exposed Set -

--	--

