### **Confidentiality Statement**

---

Data and information contained in this document are considered to constitute trade secrets and confidential commercial information, and the legal protections provided to such trade secrets and confidential information are hereby claimed under the applicable provisions of applicable law. No part of this document may be publicly disclosed without the written consent of Philip Morris Products S.A.

---

probably due to the vasoconstrictive action of nicotine on gingival vessels. Because IQOS delivers nicotine, but much reduced levels of other HPHCs, this study may help to differentiate the effects of nicotine vs the effects of HPHCs. To investigate this, it is planned to collect 1) GCF samples, to measure inflammatory components of this oral fluid when switching to IQOS compared to continuing using cigarettes, 2) buccal swabs, to perform an RNA profiling of those cells which are directly exposed to cigarette smoke or IQOS aerosol; and 3) SP samples, to assess the change of the oral microbiome when switching to IQOS compared to patients continuing using cigarettes. The analyses of GCF and buccal swabs will help to better understand the underlying mechanism of the diseases related to cigarette smoke.

The study will follow a two parallel arm randomization design with the following strata: 1) daily cigarette consumption over the month prior to V1 and 2) PD in smokers with generalized chronic periodontitis [78]. This selection is based on the fact that: 1) the degree of smoking exposure is related to the severity of periodontal destruction [25, 82] 2) pre-treatment depth of PD and CAL have been shown to affect response of therapy [83, 84].

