4.3 Product Allocation and Blinding

4.3.1 Method of Assigning Patients to Sequence/Product Arms

After all assessments of V1 have been completed, patients will be randomized to 1 of the 2 study arms; continued cigarette smoking or IQOS use. Patients will be informed about their study arm allocation at V2. Patients will be randomized in one of the two study arms, IQOS arm: cigarette arm in a 1:1 ratio using a stratified randomization.

Confidentiality Statement

Data and information contained in this document are considered to constitute trade secrets and confidential commercial information, and the legal protections provided to such trade secrets and confidential information are hereby claimed under the provisions of applicable law. No part of this document may be publicly disclosed without the written consent of Philip Morris Products S.A

Stratification:

- Daily cigarette consumption over the month (30 days) prior to V1 (10-19 cigarettes/day vs. >19 cigarettes/day)
- Disease severity (< 5 mm PD vs. \geq 5 mm PD) in smokers with generalized chronic periodontitis.

Disease severity is based on the tooth site having the most severe condition of PD.

In each arm, a quota will be applied to ensure that patients with PD \geq 5 mm represent at least 50% of the randomized patients. Arm assignment for patients with PD < 5 mm will be capped at n = 80, after which enrollment of patients with PD < 5 mm will be stopped. Patients with PD < 5 mm already enrolled but not randomized may be discontinued in order to ensure that randomization quota are met. Enrollment of patients with PD \geq 5 mm will continue until 172 patients are randomized. At this stage, patients' enrollment will be stopped and patients already enrolled but not randomized may be discontinued. In case patients are discontinued after V1, they will be referred to their dentist/general practitioner and will receive financial compensation for the visit. Patients will be informed of their randomized study arm by the study site during V2.

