9.5.1.1 Primary Analyses

Primary Analysis of Change from Baseline in PD at V4	
Population	
 • As Exposed Set For this analysis, subjects categorized in IQOS user, cigarette user or dual user will be included with initial PD \geq 4mm will be included.
	The primary analysis will be performed on the As Exposed Set using a mixed model for repeated measurements (MMRM). Estimates of difference in PD will be calculated for Cigarette User against IQOS User categories and Cigarette User against Dual User categories. The model will include the PD change from baseline as the dependent variable, adjusting for the following covariates; 
 1. Daily cigarette consumption at V1 2. Disease severity at V1 3. Full mouth PD at V1 4. Visit 5. Product use pattern (IQOS user, cigarette smoker or dual user) 6. Interaction between visit and product use

Confidentiality Statement

Data and information contained in this document are considered to constitute trade secrets and confidential commercial information, and the legal protections provided to such trade secrets and confidential information are hereby claimed under the provisions of applicable law. No part of this document may be publicly disclosed without the written consent of Philip Morris Products S.A

Primary Analysis of Change from Baseline in PD at V4

7. Average daily cigarette use at each visit
8. Interaction between Daily cigarette consumption at V1 and product use
9. Interaction between Disease severity at V1 and product use
10. Time since last SRP
11. Number of target tooth/teeth extracted
12. Number of non-measured target tooth/teeth extracted
13. Baseline tooth mobility

Site will be included as a random effect. The degrees of freedom will be adjusted by using Kenward Roger (KR) method. A Toeplitz structure (“type=toep”) will be specified as the covariance matrix. However, other covariance structures may be used in case of non-convergence. Covariates 8-12 will be assessed for adequacy in the model using a step-wise (backward) approach through the following algorithm.

1. Fit a full model using maximum likelihood with all covariates
2. Perform a likelihood ratio test for the full model and drop the covariate with the largest p-value for the likelihood ratio statistic if it is more than 0.05.
3. Drop one covariate (only covariates 7-14) and re-fit the model.

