9.5.2 Secondary Analyses

9.5.2.1 Secondary Analysis

Analysis of Change from Baseline in PD at V3 and CAL at V4 / V3	
Population	: • As Exposed Set
Contents	: The model will include the PD (or CAL) change from baseline as the dependent variable, adjusting for the following covariates; 
 • The statistical model is described in section 9.5.1. Note that “Full mouth PD at V1” will be replaced as “Full mouth CAL at V1”
Target visit	: • V3 (3 Months) for PD • V3 (3 Months) and V4 (6 Months) for CAL
Remarks	: • Statistical tests for PD at V3, CAL and V4 and V3 are performed in a sequential manner as detailed in section 9.1.8. • The same model for the primary analysis will be used with both V3 and V4 data included; PD at 3 months will be reported only if the test for PD between Cigarette User and IQOS User categories at 6 months is significant. • If the test between Cigarette User and IQOS Users Categories for PD is significant at V3, then the model with change from baseline CAL will be fitted with both V3 and V4 data and the test between CC and IQOS for CAL at V4 will be reported. • If the test between Cigarette User and IQOS User categories for CAL at V4 is significant, then the test between Cigarette User and IQOS User Categories for CAL at V3 will be reported.
Sample code	Refer to “ Primary Analysis ”
Output	15.4.7.1 Analysis of Change from Baseline in Pocket Depth (mm) at V3 with Initial Pocket Depth \geq 4 mm - As Exposed Set - 15.4.7.2 Regression Coefficients and Graphical Diagnostics of Analysis of Change from Baseline in Pocket Depth (mm) at V3- As Exposed Set - 15.4.7.3 Analysis of Change from Baseline in Clinical Attachment Level (mm) with Initial Pocket Depth \geq 4 mm - As Exposed Set -

Confidentiality Statement

Data and information contained in this document are considered to constitute trade secrets and confidential commercial information, and the legal protections provided to such trade secrets and confidential information are hereby claimed under the provisions of applicable law. No part of this document may be publicly disclosed without the written consent of Philip Morris Products S.A

Analysis of Change from Baseline in PD at V3 and CAL at V4 / V3

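### The CAL model swaps continuous baseline pocket depth for baseline CAL instead of keeping both, so initial depth is only coarsely adjusted and the supportive CAL models do not match (minor, free improvement)

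*SAP*

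**What the plan says.** SAP 9.5.2.1 covers PD at V3 and CAL at V4 and V3 in one table for the As Exposed Set. Its Contents row says "The statistical model is described in section 9.5.1" and adds "Note that “Full mouth PD at V1” will be replaced as “Full mouth CAL at V1". Its Remarks say of PD at 3 months: "The same model for the primary analysis will be used with both V3 and V4 data included".

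The other covariates of SAP 9.5.1.1 carry over to CAL. Two of them concern pocket depth:

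- Covariate 2, "Disease severity at V1". SAP 4.3.1 defines it: "Disease severity is based on the tooth site having the most severe condition of PD", cut at below 5 mm versus 5 mm or more.
- Covariate 9, "Interaction between Disease severity at V1 and product use". This one can be removed: "Covariates 8-12 will be assessed for adequacy in the model using a step-wise (backward) approach".

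The CAL endpoint is restricted to sites with initial PD of at least 4 mm (SAP 3.2). Protocol 4.1 explains the choice of strata partly by the statement that "pre-treatment depth of PD and CAL have been shown to affect response of therapy". Protocol 2.1 describes CAL as the sum of PD and gingival recession.

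For the FAS and PP sets, SAP 9.5.2.2 applies the primary-analysis model to both PD and CAL. It has no substitution note.

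**The concern.** Adjusting CAL change for baseline CAL is right. The question is why baseline PD has to leave the model to make room for it. CAL mixes pocket depth with recession: a given CAL can be a deep pocket with little recession or a shallow pocket with much. The sites analysed are chosen by pocket depth, and the protocol names pocket depth as a driver of response.

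The contrast is between product-use groups, not randomised arms, so randomisation does not protect it. If those groups differ in initial depth in a way that baseline CAL and the stratum do not capture, part of the difference passes into the estimated CAL effect. Protocol 4.1 regards CAL change as the endpoint of greatest clinical relevance, and its tests are part of the hierarchical sequence.

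Separately, if the main and supportive CAL models use different baselines, a difference between their results could come from the covariates rather than from the population.

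**Working it through.** **1. What each CAL model contains, read literally**

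| Term | As Exposed (9.5.2.1) | FAS and PP (9.5.2.2) |
|---|---|---|
| Full mouth PD at V1 | no, replaced | yes |
| Full mouth CAL at V1 | yes | no |
| PD severity stratum (covariate 2) | yes, fixed | yes, fixed |
| Stratum by product use (covariate 9) | at the start, removable | at the start, removable |

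Covariate 2 lies outside both removal ranges that SAP 9.5.1.1 gives (8-12 in the text, 7-14 in the algorithm). Covariate 9 lies inside both.

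**2. What the stratum can carry**

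PD is recorded in whole millimetres (SAP 5.1.1) and analysed sites start at 4 mm. If the worst site is below 5 mm, every analysed site is exactly 4 mm. All variation in initial depth at analysed sites therefore lies among patients whose worst site is 5 mm or more. By design they are at least 50% of those randomised (SAP 4.3.1). Within that group the two-level term is constant and captures none of the variation.

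**3. How much of full mouth PD the remaining terms may carry (illustration)**

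The documents give no PD-CAL correlation, so these inputs are assumed: normal variables; recession independent of PD, with an SD *r* = 0.5 to 1.5 times that of PD; worst-site PD correlated 0.5 to 0.9 with mean PD; stratum split at 80/172 = 46.5%.

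- Baseline CAL alone: R² = 1/(1 + *r*²), which is 1/1.25 = 0.80, 1/2 = 0.50 and 1/3.25 = 0.31 for *r* = 0.5, 1 and 1.5.
- Baseline CAL plus the stratum, by simulation: 0.81-0.84, 0.54-0.67 and 0.39-0.60.

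Under these assumptions 16% to 61% of the variance in full mouth PD is left unadjusted.

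**4. The plan's own figures**

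The plan sizes the trial for PD only (Protocol 12.2): SD 0.5 mm, difference 0.25 mm, one-sided 2.5%, power 80%. The normal formula gives 2 × (1.960 + 0.842)² × (0.5/0.25)² = 62.8, so 63; the t-test version gives 63.8, so 64. Then 64/0.75 = 85.3, so 86 per arm and 172 in total. This reproduces the plan. It gives no figure for CAL.

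**5. Precision, borrowing the PD figures for CAL (assumption)**

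With 64 per group, SE = 0.5 × √(2/64) = 0.0884, and power = Φ(0.25/0.0884 − 1.960) = 80.7%. If retained PD explains a further fraction *q* of residual variance, the SD becomes 0.5 × √(1 − *q*):

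| *q* | 0% | 2% | 5% | 10% | 20% |
|---|---|---|---|---|---|
| Power | 80.7% | 81.5% | 82.7% | 84.6% | 88.5% |

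**6. Confounding (assumption)**

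Bias = residual imbalance in PD × slope of CAL change on PD, both after the remaining covariates. An imbalance of 0.05 to 0.2 mm and a slope of 0.1 to 0.5 mm per mm give 0.05 × 0.1 = 0.005 mm up to 0.2 × 0.5 = 0.10 mm.

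**The case against.** A reader might infer that initial pocket depth is dropped from the CAL model. It is not. The severity stratum is fixed in the model, its interaction with product use is there at the start, and baseline CAL contains PD.

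A reader might also infer a conflict with the protocol. There is none. Protocol 4.1 offers its statement as the reason for the strata, and the PD stratum is kept. The same statement names CAL, so adjusting for baseline CAL agrees with it. Protocol 12.7 lists no covariates for the CAL model, so nothing is overridden. Adjusting an outcome for its own baseline is also the SAP's practice for the biomarkers and the crevicular-fluid analytes.

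A third inference is that the note, placed in a table that also covers PD at V3, strips baseline PD from that model too. The Remarks largely settle this, since they report PD at V3 from the primary model. What is left is loose wording.

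Other objections stand in part:

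- Full mouth PD averages all measured sites, including those below 4 mm, so retaining it does not adjust exactly for depth at the analysed sites. It is still the continuous depth covariate that the primary model uses.
- The plan assumes 10% non-adherence (SAP 6), and randomisation is stratified on PD severity. Use groups may therefore overlap largely with the arms, which limits the imbalance to be expected.
- The CAL tests come third and fourth in the sequence, and Protocol 4.1 warns that CAL may need more than 6 months to improve.

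Two replies are weak. The SAP's allowance for adding covariates does not pre-specify this one. Collinearity between PD and CAL mainly affects their own coefficients, not the product contrast.

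**Conclusion.** The point holds as a minor one and is a free improvement. The As Exposed CAL model has no continuous pocket-depth term. The depth stratum it keeps is constant among the patients in whom depth at the analysed sites varies, and baseline CAL is an imperfect stand-in. Because the comparison is by actual use, residual imbalance can enter the contrast, and some precision may be lost.

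The size cannot be derived from the documents. The 16-61% unadjusted variance, the power of 80.7-88.5% and the bias of 0.005-0.10 mm all rest on the assumptions shown, and the effect may be modest. A reader might reach a gain worth 4-19% more patients by assuming a partial correlation of 0.2-0.4 given baseline CAL (1/0.96 − 1 and 1/0.84 − 1). That ignores the retained stratum, so it is not the gain over the SAP's actual model.

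The mismatch between the main and supportive CAL models needs no assumption. It follows from reading SAP 9.5.2.1 and 9.5.2.2 as written.

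**What to change.** Replace the note in SAP 9.5.2.1, and repeat it in 9.5.2.2, with: *For CAL, Full mouth CAL at V1 is added and Full mouth PD at V1 is retained, identically in the As Exposed, FAS and PP analyses; for PD at V3 the primary model is used unchanged.*

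The cost is one sentence and one degree of freedom. Both baselines are already measured at V1. The change should be made before the statisticians are unblinded. If that point has passed, report the two-baseline model as a documented sensitivity analysis.

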The choice of the primary and secondary objectives are based as a selection of 1) the most published assessment, *i.e.*, reduction of PD, which has been shown to occur rather rapidly after mechanical therapy (*i.e.*, within 3 to 6 months) and is more representative of the overall inflammation, 2) the most clinically relevant endpoint, *i.e.*, CAL change, which is more representative of tissue destruction, and is thus determinant in the increased risk of tooth loss. Data on CAL change in smokers vs non-smokers or quitters, are, however, sparser than data on PD. The assessment of both parameters as primary and secondary endpoint will thus provide evidence on both the effect of IQOS on inflammation status and on tissue repair and will provide information about the modification of the healing profile related to switching to IQOS.

The limitation of use of antibiotics before and during the study is largely driven by the differential effect that those may have on healing after mechanical periodontal therapy [85], but also, to a slighter extent, because they will affect the microbial oral environment of the patients. Similarly, use of steroidal or non-steroidal anti-inflammatory drugs may affect healing [86, 87], bisphosphonates, which have been shown to be effective in periodontitis management through inhibition of the alveolar bone resorption, should be considered with care during the study because of a potential risk of osteonecrosis of the jaw [88]. Anti-coagulants should also be considered with care because of the risk of bleeding [89].

BoExp to NEQ, nicotine-derived nitrosamine ketone (NNK) (total NNAL) and acrylonitrile (CEMA) will serve as indicators of overall exposure of the patients throughout the study. These markers have relatively long half-lives, and should provide a good estimate of the exposure, even if the patient comes early in the morning for his/her visit. Because nicotine is expected to be delivered with IQOS at levels comparable to cigarettes, levels of NEQ are not expected to be lower in IQOS users than cigarette users, but it will serve as an overall estimate of exposure

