**Table 7 Sample sizes for PD differences between smokers and non-smokers and standard deviations based on the literature**

SD \ difference (mm)	0.2	0.25	0.3	0.35
	0.4	64	42	29
0.45	81	52	37	27
0.5	100	64	45	33

Abbreviation: SD = Standard deviation

Thus, the sample size selected above gives sufficient power for testing PD.

With alpha of 2.5%, power of 80%, SD of 0.5, and effect difference of 0.25 mm, then sample size needed in each arm is 64 patients. By considering 25% of drop out and product switching, 86 patients per arm, i.e., 172 patients in total, are needed.

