9.1.8 Multiple Comparison/Multiplicity

There will be an adjustment for multiplicity for the secondary testing of CAL and PD within the As Exposed Set, as well as for BoExp. PD at 3 months and CAL at 6 and 3 months will be tested in a hierarchical manner, depending on the outcome of the test at previously specified endpoint in hierarchical testing order. The order of testing is as follows,

The primary analysis, of PD at 6 months will be tested using a one-sided alpha level of 2.5%.

1. PD at 6 months will be tested.

The secondary analysis of PD at 3 months and CAL at 6 and 3 months will be tested in a hierarchical manner, using a one-sided alpha level of 2.5%, depending on the outcome of the test at previously specified endpoint in hierarchical testing order.

1. PD at 3 months will be tested only if the test for PD at 6 months is significant.

2. CAL at 6 months will be tested only if the test for PD at 3 months is significant

3. CAL at 3 months will be tested only if the test for CAL at 6 months is significant.

Additional secondary analysis of the BoExp will be tested, in a hierarchical manner within each BoExp (independent of the other statistical tests being performed), using a one-sided alpha level of 2.5%. The hierarchical order will be:

1. BoExp at 6 months will be tested.

2. BoExp at 3 months will be tested only if the test for BoExp at 6 months is significant.

Total NNAL and CEMA levels (concentration data adjusted for creatinine), analyzed on a logarithmic scale, will be tested at 6 and then 3 months, in that order, so that the testing of each BoExp will stop if the test is not significant.

Confidentiality Statement

Data and information contained in this document are considered to constitute trade secrets and confidential commercial information, and the legal protections provided to such trade secrets and confidential information are hereby claimed under the provisions of applicable law. No part of this document may be publicly disclosed without the written consent of Philip Morris Products S.A

Unless stated otherwise, all statistical tests will be one-sided and conducted at the 2.5% level, and all CIs will be two-sided 95%.

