Analysis Variables	: 
 • NEQ adjusted for creatinine • Total NNAL adjusted for creatinine • CEMA adjusted for creatinine
Target visit	: 
 • Baseline • V3 (3 months) • V4 (6 months)
Remarks	: 
 • Statistical tests for each BoExp at V3 and V4 performed in a sequential manner as detailed in section 9.1.8. • The same model for the analysis will be used with both V3 and V4 data included, if the test between CC and IQOS is significant at V4 then the test between CC and IQOS for V3 will be reported in the same table.
Sample code	Refer to " Primary Analysis "
Output	
15.4.7.5 Analysis of Relative Change from Baseline in NEQ (mg/g) (Biomarkers of Exposure) (Geometric LS means, Ratio of Geometric Means and p-value) - As Exposed Set -
 
15.4.7.6 Regression Coefficients and Graphical Diagnostics of Analysis of Relative Change from Baseline in NEQ (mg/g) (BoExp) Geometric Mean Value - As Exposed Set -
 
15.4.7.7 Analysis of Relative Change from Baseline in Total NNAL (pg/mL) (Biomarkers of Exposure) (Geometric LS means, Ratio of Geometric Means and p-value) - As Exposed Set -
 
15.4.7.8 Regression Coefficients and Graphical Diagnostics of Analysis of Relative Change from Baseline in Total NNAL (pg/mL) (Biomarkers of Exposure) Geometric Mean Value - As Exposed Set -

Confidentiality Statement

Data and information contained in this document are considered to constitute trade secrets and confidential commercial information, and the legal protections provided to such trade secrets and confidential information are hereby claimed under the provisions of applicable law. No part of this document may be publicly disclosed without the written consent of Philip Morris Products S.A

Summary Table of Analysis for BoExp Geometric mean value

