9.5.2.2 Supportive Analysis for Secondary Objectives

Summary Table of Supportive/Sensitivity Analyses to Evaluate the Change from Baseline in PD at V3 / CAL at V3 and V4

Population	:	
 • Full Analysis Set • Per Protocol Set
Contents	:	
The model will include the either PD or CAL change from baseline as the dependent variable, adjusting for the following covariates;
 
 • The same model described in “Primary Analysis” will be used.
Target visit	:	
 • V3 (3 Months) for PD • V3 (3 Months)/ V4 (6 Months) for CAL
Remarks	:	
 • Statistical tests for PD at V3, CAL and V4 and V3 are performed in a sequential manner as detailed in section 9.1.8. • The same model for the primary analysis will be used with both V3 and V4 data included, PD at 3 months will be reported only if the test for PD between CC and IQOS at 6 months is significant. • If the test between Cigarette User and IQOS User categories for PD is significant at V3, then the model with change from baseline CAL will be fitted with both V3 and V4 data and the test between Cigarette User and IQOS User categories for CAL

Confidentiality Statement

Data and information contained in this document are considered to constitute trade secrets and confidential commercial information, and the legal protections provided to such trade secrets and confidential information are hereby claimed under the provisions of applicable law. No part of this document may be publicly disclosed without the written consent of Philip Morris Products S.A

Summary Table of Supportive/Sensitivity Analyses to Evaluate the Change from Baseline in PD at V3 / CAL at V3 and V4

	
at V4 will be reported.
 
 If the test between Cigarette User and IQOS User categories for CAL at V4 is significant, then the test between Cigarette User and IQOS User categories for CAL at V3 will be reported.
Sample code	Refer to " Primary Analysis "
Output	
15.4.8.1 Analyses of Change from Baseline in Clinical Attachment Level (mm) with Initial Pocket Depth \geq 4 mm - Full Analysis Set, Per Protocol Set -
 
15.4.8.2 Regression Coefficients and Graphical Diagnostics of Analysis of Change from Baseline in Clinical Attachment Level (mm) - Full Analysis Set, Per Protocol Set -

Summary Table of Supportive/Sensitivity Analyses for BoExp Geometric Mean Value

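### The SAP makes fitting of the CAL model, and reporting of the 3-month PD and CAL contrasts, depend on earlier significance; the hierarchy should decide only which tests are confirmatory

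*SAP*

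**What the plan says.** Protocol 12.1.5 and SAP 9.1.8 set a fixed testing order: PD at 6 months, PD at 3 months, CAL at 6 months, CAL at 3 months, each at one-sided 2.5%. Both make the *test* of each endpoint conditional on the one before.

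The remarks in SAP 9.5.2.1 add three further conditions:

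- **PD at 3 months:** "PD at 3 months will be reported only if the test for PD between Cigarette User and IQOS User categories" at 6 months is significant.
- **CAL model:** if the comparison "for PD is significant at V3, then the model with change from baseline CAL will be fitted with both V3 and V4 data", and the 6-month CAL test is then reported.
- **CAL at 3 months:** reported if CAL at 6 months is significant.

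SAP 9.5.2.2 carries the same conditions into the supportive sets: "PD at 3 months will be reported only if the test for PD between CC and IQOS at 6 months is significant". SAP 9.5.1.2, however, lists both 3 and 6 months as target visits for the PD model in those sets, with no condition.

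For the biomarkers, the SAP 9.5.2.1 remarks say that "if the test between CC and IQOS is significant at V4 then the test between CC and IQOS for V3 will be reported". The contents row of the same table promises geometric LS means, their ratios and 95% intervals at both visits, with no condition.

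Protocol 12.7 states that the 3-month PD analysis and both CAL analyses will be performed, with supportive analyses in the FAS and PP sets. SAP section 7 lists two changes from the protocol (the As Exposed Set definition and removal of the Adherent Use Set). Conditional fitting or reporting is not among them.

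**The concern.** A fixed sequence limits which p-values can support a claim. It gives no reason to leave a pre-specified secondary endpoint unestimated, because showing a difference and its interval rejects no hypothesis.

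CAL change in sites with initial PD of 4 mm or more is a named endpoint under the first secondary objective. Protocol 4.1 ranks CAL above PD for clinical relevance: "CAL change, which is more representative of tissue destruction, and is thus determinant in the increased risk of tooth loss". Under the SAP rule, a PD result that misses significance at 6 or 3 months leaves CAL with no adjusted comparison, whatever CAL itself did and in whichever direction. A reader of a neutral PD result would then lack the estimate most useful for interpreting it.

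**Working it through.** **1. The plan's own figure.** Protocol 12.2 gives the inputs "With alpha of 2.5%, power of 80%, SD of 0.5, and effect difference of 0.25 mm" and concludes that the "sample size needed in each arm is 64 patients". The level is confirmed in SAP 9.1.8: "The primary analysis, of PD at 6 months will be tested using a one-sided alpha level of 2.5" percent.

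- Normal approximation: n = 2 × 0.5² × (1.960 + 0.842)² / 0.25² = 62.8, so 63.
- Two-sample t-test (noncentral t): 64 per arm, power 80.1%.
- Allowing for 25% dropout and switching: 64 / 0.75 = 85.3, so 86 per arm and 172 in total.

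The stated 64, 86 and 172 are reproduced. They serve here only to fix the power of the PD tests that open or close the gate.

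**2. What each condition removes.**

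| Result | Model fitted? | Contrast reported? |
|---|---|---|
| PD, 3 months | Always (same model as the primary analysis) | Only if PD at 6 months is significant |
| CAL, 6 months | Only if PD is significant at 6 and then 3 months | Whenever the model is fitted |
| CAL, 3 months | As CAL at 6 months | Only if CAL at 6 months is also significant |
| Biomarkers, 3 months | Always | Estimates and intervals always; test only if significant at 6 months |

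**3. Probability that the CAL model is not fitted.** The standard error of a PD difference is 0.5 × √(2/64) = 0.0884 mm. The two PD statistics are treated as bivariate normal with means d₆/0.0884 and d₃/0.0884, unit variances and correlation ρ. The CAL model is fitted when both exceed 1.960, so the probability sought is 1 − P(Z₆ > 1.960 and Z₃ > 1.960).

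The documents give no separate 3-month effect and no correlation between visits. Both are assumptions and are shown as ranges. With d₆ = 0.25 mm (mean 2.83):

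| Assumed 3-month effect | Mean of Z₃ | ρ = 0 | ρ = 0.5 | ρ = 0.7 | ρ = 0.85 |
|---|---|---|---|---|---|
| 0.25 mm | 2.83 | 35% | 30% | 28% | 25% |
| 0.20 mm | 2.26 | 50% | 44% | 42% | 40% |
| 0.15 mm | 1.70 | 68% | 63% | 61% | 61% |

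The ρ = 0 entry in the first row can be checked by hand. Each test has power Φ(2.83 − 1.96) = 0.807, and 1 − 0.807² = 0.348.

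**4. No PD effect at 6 months.** The first test is significant with probability 2.5%, so the CAL model is unfitted with probability at least 1 − 0.025 = 97.5%.

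**5. PD contrast at 3 months.** At the design effect it goes unreported whenever the primary test fails, which is about 20% of the time.

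**6. Effect of removing the gate.** The first test in the chain still has one-sided level 2.5% and nothing later can be claimed without it, so the family-wise error of the PD/CAL chain stays at 2.5%. The sample size is unchanged.

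**The case against.** The strongest reply is that the rule is pre-specified and visible, leaves the primary test untouched, and is surrounded by output that carries no condition. Several stronger readings that a reader might take from the wording do fail:

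- **That 3-month biomarker results would be lost.** One model with both visits is fitted without condition, and SAP 9.5.2.1 promises the 3-month ratios and intervals. Only the 3-month test is conditional, as in Protocol 12.1.5.
- **That PD at 3 months would not be analysed.** The primary model includes both visits, and its regression coefficients are a planned output (15.4.5.2). Only the reporting of the 3-month contrast is conditional.
- **That non-significant results are suppressed.** The gate acts on the preceding test. The first non-significant result in the chain is reported; those after it are withheld whatever their own p-values.
- **That a benefit confined to PD would hide CAL.** If PD is significant at both visits, the CAL model is fitted and the 6-month CAL result is reported even if it is null. Only CAL at 3 months is then withheld.
- **That no CAL data would be shown.** Full-mouth CAL (15.2.7.1), CAL by initial PD class at both visits (15.2.7.3) and plots (15.1.7.9, 15.1.9.5) carry no condition. The four classes from 4 mm upward together cover all the endpoint's sites.
- **That no analysis set could supply an estimate.** SAP 9.5.2.2 does not say whether the FAS and PP gates use the As Exposed result or each set's own. If each set's own, the loss occurs set by set.

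These points narrow the concern but do not remove it. The descriptive tables pool neither the PD classes nor the adjustment, and none gives an adjusted group difference. The SAP introduction allows supplementary analyses documented in the study report, but that is a permission and does not commit the sponsor to the CAL estimate.

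**Conclusion.** The concern holds for CAL and for the 3-month PD contrast. Followed as written, SAP 9.5.2.1 and 9.5.2.2 can leave a named secondary endpoint without an adjusted between-group estimate or interval in the analysis set concerned. This departs from Protocol 12.7 and is not declared in SAP section 7.

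At the design effect in both visits the CAL model goes unfitted with probability about 25-35%; with a 3-month effect of 0.20 mm, about 40-50%; with no 6-month PD effect, at least 97.5%. The group size, SD and 0.25 mm effect are the plan's. The 3-month effects and the correlations (0 to 0.85) are assumptions, and the figures describe one gate in one analysis set using a simple two-group comparison in place of the full mixed model.

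There is also a direct inconsistency: SAP 9.5.1.2 and 9.5.2.2 cannot both be followed for PD at 3 months in the FAS and PP sets when the 6-month test fails. This is a reporting defect; the primary analysis, its error rate and the sample size are unaffected.

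**What to change.** In the remarks of SAP 9.5.2.1 and 9.5.2.2, replace the conditional fitting and reporting statements with text to this effect: *The PD and CAL models are always fitted. LS-mean differences with two-sided 95% confidence intervals at V3 and V4 are always reported for the As Exposed, FAS and PP sets. The order in section 9.1.8 determines only which tests are confirmatory; tests after the first non-significant one are labelled descriptive.*

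Two consistency edits go with this:

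- Align 9.5.1.2 with 9.5.2.2, so that PD at 3 months in the FAS and PP sets is reported without condition.
- State in the biomarker remarks of 9.5.2.1 that the condition applies only to the 3-month test, since the 3-month ratios and intervals are presented in any case.

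The cost is SAP wording and minor output work. The SAP already lists model tables for PD and CAL (15.4.6.1, 15.4.7.1, 15.4.7.3 and 15.4.8.1). No alpha is spent and no patients are added.
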